By contrast interventions for couples with a member suffering from combat-related PTSD are accumulating an evidence base. Improved symptom and relationship outcomes from couplesbased treatments for PTSD (e.g., Cognitive- Behavioral Couples Treatment (CBCT)-Monson et al., 2004, 2012; Structured Approach Therapy (SAT)-Sautter et al., 2009) lend support to involving partners in an intervention that aims to rehabilitate Veterans with [a history of] mTBI given the comorbidity between these two conditions. Our treatment model in fact shares common elements with CBCT and SAT including psychoeducation, enlisting the support of the partner in rehabilitation and a focus on communication. However, whereas the PTSD treatments focus on strengthening the marital relationship as a foundation for exposure exercises aimed at symptom reduction, MFG-mTBI-C promotes empathic acceptance of and helping to compensate for the Veterans' cognitive limitations. Communication skills training (CST) in CBCT and SAT assumes intact cognitive functioning in emotion recognition and processing, whereas CST in MFG-mTBI-C starts by developing strategies to assess and compensate for deficits in emotion processing as a prerequisite to learning more advanced skills: The unique challenges that Veterans with a history of mTBI confront in developing skills to communicate with their spouses/partners underscores the need for couples' interventions addressing the specific rehabilitation needs of these Veterans. The proposed research aims to fill this critical gap in research on interventions targeting Community Integration among OEF/OIF/Persian Gulf Veterans with a history of mTBI and their families. Finally, in addition to promoting community integration, if effective, this intervention could help stem the tide of intimate partner violence, hazardous drinking and divorce that is threatening this country's Veterans and their families.

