
Treatment: Multi-Family Group for mTBI (MFG-mTBI-C) consists of three sequential phases: 1) "Joining" in which the educator meets with each individual family for 2-3 sessions to evaluate ongoing problems and define treatment goals; 2) An Educational Workshop which provides information about TBI to all Veterans and families; 3) bi-monthly multifamily group meetings for 6 months (12 sessions) which provide a structured format for building problem-solving and communication skills. The educator joining with each couple also leads the group. The first two phases take approximately 2 months, for a total of 8 months of intervention. The group sessions consist of 3 components: (1) A brief (15-minute) period for socialization, unwinding and "small talk"; after 15 minutes the educator starts the "Go Round" (2) in which each couple relate briefly how the past two weeks have gone for them, including follow-up on homework or problemsolving recommendations. The educators take this opportunity to amend plans which have not been successful, offering a modification of the original or an alternative solution. Based on the Go Round, a problem or goal is selected for the current week's group exercise. Thirty-five minutes are allotted to the Go Round, including problem selection. (3) The educators then lead the group in formal problem solving, using a six step process based on brainstorming methods from organizational and business practices. Approximately thirty-five minutes are allowed to complete this process, specified below. The proceedings should be recorded on a whiteboard, to facilitate group participation and record the results.

- **Step 1.** Define the problem or goal. (MFG members & educators);
- Step 2. List all possible solutions. (All MFG members);
- **Step 3.** Discuss advantages and disadvantages of each in turn. MFG members & educators);
- **Step 4.** Choose the solution that best fits the situation. (Family);
- Step 5. Plan how to carry out this solution. (Family & educators); and
- **Step 6.** Review implementation. (Educators).

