Comparison Condition: Group Health Education: The Group Health Education (GHE) condition is a 14-session, highly structured educational intervention providing general information on health problems that are common among the general OEF/OIF/Persian Gulf cohort including sleep and sleep problems, physical activity and exercise, and alcohol and drug use, as well as general guidelines for improving health behavior in these areas. Areas of focus in MFG-mTBI-C such as coping with Veterans' memory problems or couples and family readjustment issues are explicitly not addressed in GHE. Each session follows the same structure, beginning with a presentation of the objectives for the current session and a brief review of material from the previous session before introducing the session's topic and presenting information on two to six major points. In order to limit opportunities for group interaction and development of group cohesion, GHE utilizes a traditional didactic model with information delivered by the educator in a classroom or lecture setting (where all chairs face the educator), where the information provided is general and broad-based rather than focused on individual participants' concerns. To avoid overlap with MFG problem-solving skills training. individual health problems will not be discussed: participants will be referred to their provider or supplied with a referral as needed. By contrast, MFG-mTBI-C delivers skills training in a roundtable setting where all group members are encouraged to join in problem-solving exercises, the educator's approach is collaborative and materials are drawn from the everyday problems brought in by members, designed to foster group cohesion and support. Consistent with an educational model, handouts summarizing session material are provided in GHE-C but homework is assigned only in MFG-mTBI-C, as an integral feature of skills training and of our adaptation of multifamily group for mTBI where rehearsal and repetition are critical components of skills acquisition. Table 6 shows the key structural-conceptual differences between conditions, while Table 7 summarizes the overall structure of the two conditions, including the different phases, components and basic material delivered in each intervention. Table 7 demonstrates the 2 conditions are identical in # sessions and overall structure (multifamily group sessions following individual couples "Joining" sessions), but differ in treatment strategies (skills training vs. general education without reference to or problem-solving about participants' individual health concerns/behavior. As with MFG-mTBI-C, the educator joining with the couple is also the group leader. To accommodate difficult schedules that often include work, school, and/or childcare, we offer participants to call-in to groups from a private space, such as a bedroom or private office, to maintain confidentiality.

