
Table 6: Comparison of MFG-mTBI-C and Control Treatment (GHE)

Treatment Component	MFG-mTBI-C	GHE (Control)	
Therapeutic Strategy	Skills training	Information only	
Contents	Compensation for TBI-related deficits in emotion processing, memory/planning	Building a healthy lifestyle	
Target Group	OEF/OIF/Persian Gulf Veterans with TBI/partners	All OEF/OIF/Persian Gulf Veterans/partners	
Use of Group Dynamics/ Cohesion	Social support promoted:  Entire group participates in problemsolving for each couple and gives support and encouragement	Social support minimized:  Because individual health issues are not discussed, education is general and group interaction minimized	
Therapeutic Stance	Educator stance is collaborative	Educator stance is didactic	
Room Set-up	Round table	Lecture style (all chairs face forward)	
Source of Material	Drawn from everyday problems brought in by group members	Supplied by educator	
Homework	Assigned and reviewed and the start of the following session	Handouts but not homework provided	

Table 7: Comparison of MFG-mTBI-C and Control Treatment (GHE)

Treatment Component	MFG-mTBI-C	# sessions	GHE (Control)	# sessions
Joining	Couples-tailored Education:* Normalization of couples conflict, misattribution of TBI deficits corrected.  Skills Training: Recommend 1+ compensatory strategies, basic communication training exercise.  Formulation of problems in coping & communication patterns	2(3)**	Standard Couples Intake: History of Veteran, partner and couple, focusing on current health, activities, sleep patterns, diet, medications and other health behaviors. No skills training, cognitive interventions or formulation of couples' functioning.	2(3)**
Multifamily Group Sessions	Educational Workshop: TBI: pathogenesis, behavioral sequelae, comorbidities, treatment, prognosis and family impact. Structure and function of multifamily group, how it can help.	2	Health Education Introduction: Structure and rationale for intervention. Rules of conduct. Overview of topics to be covered.	1
	Problem-solving Sessions: Skills training: Problem-solving designed to address specific problems associated with mTBI. Compensatory strategies for memory problems, planning. Disability-adapted communication training.	12	Group Health Education: Information provided to promote healthy living in areas relevant for Veterans and partners (sleep hygiene, nutrition, use of alcohol, drugs, safe exercise). Personal health concerns not discussed-referred to provider.	13

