Exclusion criteria for Veterans and partners:1) a lifetime diagnosis of a major psychiatric disorder (schizophrenia, schizoaffective or bipolar disorder) or active psychosis based on the Structured Clinical Interview for DSM-IV-TR (SCID-L) (First et al., 2007); 2) alcohol or drug abuse or dependence within the past three months defined by a Short Michigan Alcoholism Screening Test (SMAST) (Selzer, 1975) ≥ 3, based on the recommended cut-off for TBI survivors (Gentilello et al.,1995) or a Drug Abuse Screening Test-10 (DAST-10) (Skinner, 1982) ≥3; 3) "severe" inter-partner violence as defined by the revised 20-item Conflict Tactics Scale

Short Form (CTS2S) (Straus & Douglas, 2004);4) a suicide attempt (actual, aborted, or interrupted) within the past six months indicated on the Columbia Suicide Severity Rating scale (C-SSRS); 5) medical condition or life event (e.g., ongoing or pending legal action in another state) that would compromise participation; 6) participation of either the caregiver or Veteran in another psychosocial intervention trial for couples six months prior to or during study or follow-up. Participation in individual psychotherapy, individual couple's psychotherapy, and pharmacotherapy are permitted: use of and starting/stopping these services will be tracked. Participants will be screened for inclusion/exclusion as described above immediately after giving consent.

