## 6.0 Reporting

This project will be monitored by a Data and Safety Monitoring Board (DSMB) because the Veterans have either been diagnosed with mTBI, a mild cognitive impairment, PTSD, and/or have reported moderate-severe PTS or CS. Thus, while the risk in this study is minimal, these Veterans can be considered a vulnerable population. The board will be composed of persons not affiliated with this pilot intervention who are experienced in various aspects of the conduct of clinical trials for persons with mTBI, or with research on PTSD or associated conditions. Because the safety risk is judged to be minimal, we propose to submit a quarterly report of aggregate data to DSMB members rather than attempt an interim analysis of efficacy and safety data by treatment assignment. The report will contain screening data, baseline demographics, retention data, number of participants removed due to clinical deterioration, serious adverse events data, as well as accruable status including projections and times to milestones. Based on this report, each DSMB member will complete a form making one of two recommendations: 1) continue recruitment as planned; or 2) schedule formal DSMB meeting immediately. If any DSMB member recommends a meeting, this will be scheduled within one week, minutes will be kept, the report will be reviewed with the PI, and the committee will vote on whether the study should: 1) continue recruitment unchanged; 2) continue with a protocol amendment; 3) stop recruiting pending further investigation. If, after this meeting, any DSMB member votes to stop recruitment, each site's IRBs will be informed. All SAEs will result in completion of an SAE reporting form and a verbal report to the Principal Investigators ([name]). Within 24 hours, the following additional individuals will be notified: 1) all Consulting Investigators and Senior Clinicians; 2) all Core Clinical Investigators; 3) The VA Institutional Review Board; 4) the DSMB. These same individuals will receive a copy of the SAE form within one week at which point a decision will be made whether to convene a meeting of the DSMB. Communication of recommendations and decisions from all parties are made back to the investigator in a timely manner. We will report all protocol amendments or changes in the informed consent to the VA IRB, as well as any temporary or permanent suspension of participant accrual.

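### Harms are sought differently in the two arms and no SAE enquiry is scheduled, so events in the GHE arm may be under-recorded

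*Combined protocol and SAP*

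**What the plan says.** **MFG-mTBI-C sessions** (5.1, Treatment). Each group session has a Go Round "in which each couple relate briefly how the past two weeks have gone for them, including follow-up on homework". It takes 35 minutes, including choice of the problem to work on. Material comes from members' everyday problems (Table 6).

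**GHE sessions** (5.1, Comparison Condition, and Tables 6 and 7). In these sessions "individual health problems will not be discussed: participants will be referred to their provider or supplied with a referral as needed". Table 7 repeats the rule: "Personal health concerns not discussed-referred to provider". The section adds that "couples and family readjustment issues are explicitly not addressed in GHE", and Table 6 says that group interaction is kept to a minimum.

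**SAE handling** (6.0). "All SAEs will result in completion of an SAE reporting form and a verbal report to the Principal Investigators", followed by notification of the IRB and the DSMB, among others. The DSMB receives a quarterly report of aggregate data, not split by arm.

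**Partner violence** (5.4). Couples are excluded for severe "inter-partner violence as defined by the revised 20-item Conflict Tactics Scale" (Short Form, CTS2S). Table 5 does not list the CTS2S at post-treatment or at 6 months. The suicide rating scale (C-SSRS) is likewise used only at screening.

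**Sources common to both arms** (5.1, Table 5 and 5.5). Blinded research assistants (RAs) give the Service Use Checklist, the MINI and symptom scales at all three assessments. VA records are examined for medication and mental health service use among Veterans enrolled in VA mental health services.

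**The concern.** Section 6.0 begins at the point where an SAE is already known. How it becomes known is left to chance disclosure, and the chance is not the same in the two arms. MFG-mTBI-C couples are regularly invited to say what has happened to them. GHE couples attend lectures in which personal health and couple matters are off the agenda and are directed to an outside provider, and no route is described for that information to return to the study.

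Two things are at stake. Control-arm events could go unseen by the investigators and the DSMB in Veterans whom Section 6.0 itself regards as vulnerable. And if harms are later tabulated by arm, as a trial report may well do, the table would carry a difference in recording that readers could take for a difference in risk. Because the DSMB sees only pooled data, such an imbalance would not show during the trial.

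**Working it through.** The plan states no figure for harms, so there is none to reproduce. The check counts the opportunities for enquiry in each arm and then asks what the common sources can recover.

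1. **Number of contacts** (Table 7, default of two Joining sessions). MFG-mTBI-C: 2 + 2 + 12 = 16. GHE: 2 + 1 + 13 = 16. Contact is equal, so the arms differ in what is asked, not in how often couples are seen.

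2. **Scheduled in-session enquiry about recent events, group phase.** MFG-mTBI-C: 12 of 14 group sessions (the problem-solving sessions; the other 2 are the educational workshop). GHE: 0 of 14 (1 introduction and 13 lectures).

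3. **Share of follow-up affected.** Section 5.1 gives about 2 months for Joining and workshop, then 6 months of problem-solving sessions, so about 8 months of intervention. The last visit is 6 months later: 8 + 6 = 14 months. The unequal enquiry covers 6/14 = 43%. The Joining phase is not counted, because the GHE intake also takes a history of the couple and their current health (Table 7).

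4. **Arm-neutral visits after baseline** (Table 5). There are 2 in each arm. Listed at those visits: SAE question 0, CTS2S 0, C-SSRS 0.

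5. **What the common sources reach.**
   - *Service Use Checklist:* inpatient and outpatient use, both members, both arms. For partners, Section 5.5 gives a look-back of 6 months. Against about 8 months of intervention, at least about 8 − 6 = 2 months before the post-treatment visit are not covered.
   - *MINI:* current and past psychiatric episodes, both members, both arms.
   - *VA records:* only Veterans in VA mental health services, and only medication and mental health service use; not partners.
   - *Couple measures* (5.5): satisfaction, conflict, communication, empathy and coping. None is described as measuring violence.
   - No section says that a finding from any of these goes onto an SAE form.

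6. **Size of any bias.** With equal true risk r in both arms and capture probabilities c_M (MFG-mTBI-C) and c_G (GHE), the ratio of recorded risks is (r × c_M)/(r × c_G) = c_M/c_G. It is 1 if capture is equal and exceeds 1 if capture is lower in GHE. The documents give neither c_M nor c_G, so no numerical bias can be derived from them.

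**The case against.** Several points on the other side are sound.

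- **The GHE rule limits content, not reporting.** Its stated purpose is to avoid overlap with skills training. Nothing stops a participant mentioning an event or an educator filing an SAE form. Section 6.0 covers all SAEs, and Section 8.0 puts them on the weekly agenda at every site. Educator calls after missed meetings (5.1) are not confined to one arm. A reader might infer that GHE events *will* be missed; the text supports only that they *may* be.
- **The Go Round is not a harms interview.** With 3 to 8 couples, 35 minutes gives at most 35/3 = 11.7 to 35/8 = 4.4 minutes each, less time for homework and problem selection, with the partner and other couples present. High capture of violence there cannot be assumed.
- **No harms comparison by arm is planned.** Section 5.6 contains none, so no planned analysis is biased.
- **Partner violence is not a study endpoint.** The Introduction remarks that "if effective, this intervention could help stem the tide of intimate partner violence, hazardous drinking and divorce", and a reader might take this as an intended inference that the trial cannot support. It is background: no violence outcome appears in the aims, the hypotheses or the listed outcomes.
- **Risk is judged minimal** (6.0), and severe violence is excluded at entry (5.4).

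What remains is that permission to report is not the same as being asked. One arm is asked regularly and the other is not, and the common sources fill the gap only in part.

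**Conclusion.** The point holds as one about completeness and even-handedness of safety capture. Ascertainment differs by arm by design: 12 scheduled in-session enquiries against none, over about 6 of roughly 14 months. No SAE enquiry is scheduled in either arm, and partner violence is not measured after screening. Events in GHE may be under-recorded. The Service Use Checklist, the MINI and VA records reduce the problem, but none is tied to SAE reporting.

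The conclusion rests on the text and the session counts, not on any assumed event risk or capture rate; the size of any bias is unknown and could be nil. The primary and secondary efficacy analyses are not affected. The change is worth making because it is cheap and because a later table of harms by arm could not otherwise be read with confidence.

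**What to change.** Amend Section 6.0 and Table 5 as follows.

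1. At the existing post-treatment and 6-month visits, the blinded RA puts the same short scripted SAE question to each member of the couple separately, in both arms, covering the whole time since the previous assessment.
2. State that an SAE found through the Service Use Checklist or the MINI is entered on the SAE form.
3. State that any tabulation of harms by arm uses these arm-neutral sources. Events that surface in sessions still go to the IRB and DSMB, but are listed separately by source.
4. Optionally, repeat the CTS2S at the same two visits in both arms.

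**Cost.** Items 1 to 3 add a few minutes to visits now planned at 80–95 minutes for Veterans and 75 minutes for partners, with no new visits or staff. GHE content and sample size do not change. Asking the question after the outcome measures would limit any risk to the blind. Item 4 adds a 20-item scale for two people at two visits and obliges the sponsor to specify how positive responses are handled, which is why it is optional.

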#### **5.2 Recruitment Methods**

Veteran participants (n=150) will be identified in one of two ways. Study staff will work closely with the clinics and programs within the site hospitals (JJP VAMC, VANYHHS, VAMHCS, DCVAMC), such as poly trauma, PTSD and mental health clinics, primary care, caregiver support programs, OEF/OIF/OND services, and other relevant clinics. Potential participants will be identified based on deployment history to Iraq/Afghanistan, a positive DVBIC screen or if they either meet diagnostic criteria for PTSD or have trauma- or CS of at least moderate severity, and cohabitation with a spouse/partner. Clinicians will then discuss study participation with identified study candidates during a routine clinical visit. Clinicians who obtain verbal consent from Veterans during a routine clinical visit may contact research staff by page to effect an in-person introduction if the clinician and the Veteran agree to this method. As an alternate method, for Veterans who agree to be contacted by the study team, the clinician will hand deliver identifying and preferred contact information to approved research staff. Research staff will then attempt to contact the Veteran using his/her preferred phone number. Veterans will also be recruited within the site hospitals via study fliers and study pocket cards posted/distributed around the site hospitals. Veterans who initiate contact do not need clinician approval but study staff will contact the Veteran's provider with his/her consent to ensure participation would not compromise healthcare. In addition, we will conduct community outreach efforts to Vet Centers, local universities and colleges, and local Community Based Outpatient Centers (e.g., White Plains CBOC), which we will visit in-person to present the study and to supply the relevant contacts persons our study fliers/pocket cards to distribute to potential candidates. All referrals made from non-VA settings will have to be enrolled at VA; otherwise, we will not consider them as eligible participants. No referrals will be made via email. All Veterans referred who express interest in the study will be asked for consent to invite their spouse or partner to participate in an information session about the study. The spouses or partners of consenting Veterans will be approached in one of two ways: 1) the Veteran may either describe the study to their spouse/partner with the assistance of the IRB-approved flier (attached as a supplement), or, 2) if the Veteran prefers, an appointment can be made for the research staff to contact the Veteran and his/her spouse/partner at a convenient time during which the staff member will describe the study and determine interest in participation. The pilot study's initial protocol left the full responsibility of describing the study to the caregiver to the Veteran. However, we discovered that using this method Veterans reported difficulty and/or burden due to the cognitive limitations and disabilities associated with mTBI. The Veterans expressed a preference for the research staff to describe the study in a consultation with their spouse partner. Based on this feedback, we amended our IRB protocol in the pilot study to allow study staff to describe the study to the spouse/partner and the Veteran in an information session at the couple's convenience. We therefore propose to provide Veterans with the two

aforementioned options. There will be no cold-calling. Any calls will be approved by the Veteran for a time where he/she and/or the spouse/partner can be present. This procedure will be followed in order of referral until the target number of cases have been consented and enrolled. Pooling data from 2010 OEF/OIF intake in VISN 2 South and the current poly-trauma clinic census in VISN 5, the estimated ethnic/racial breakdown of the study sample is 53% Caucasian, 30% African American, 15% Hispanic and 2% Asian/Pacific Islander. The Diversity Committee will recommend and help implement novel recruitment and outreach strategies to ensure overall diversity and increase the numbers of Hispanic Veterans and families seen, in particular. Participants will each be paid \$45 each time they complete an assessment (pre-treatment, post-treatment, and 6 months post-treatment).

